10.4 Primary Objective

To determine the feasibility of recruiting 72 ARDS patients across sites given 1 year of active enrolment per site, as well as assess the rate of participant recruitment and understand the barriers to enrolment.

10.5 Primary Endpoint

Record total number of patients randomized, total number of patients eligible yet not randomized, and the number of active randomizing sites on a monthly basis. This will include evaluating the validity and impact of inclusion and exclusion criteria, trial acceptability, and the reasons for lack of consent or withdrawal.

10.6 Secondary Objectives

- To assess adherence to our explicit mechanical ventilation protocols, with particular focus on delivered tidal volumes in both groups and estimated ΔP_{L-dyn} in the ECMO group
- To measure and understand the reasons for crossovers in each group

10.7 Secondary Endpoints

- Evaluate number of protocol deviations and their causes (control group: $V_T > 8 \text{ ml/kg}$, $P_{PLAT} > 30 \text{ cm H}_2\text{O}$; experimental group: $V_T > 8 \text{ ml/kg}$, $P_{PLAT} > 30 \text{ cm H}_2\text{O}$, $\Delta P_{L-dyn} > 23 \text{ cm H}_2\text{O}$) over 2 consecutive data points for a minimum of 48 hours.
- Classify crossovers as consistent with, or in deviation of, the study protocol and detailed documentation will be required for crossovers classified as deviations.

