5.3.2 Exclusion Criteria

1. Patients over 65 years of age.
2. Currently receiving any form of ECMO (ex. venovenous, venoarterial, or hybrid configuration).
3. $\Delta P_{L-dyn} \leq 20$ or Static $\Delta P \leq 15$ cmH₂O while receiving V_T 6mL/kg (i.e. normalized elastance < 2.5 cmH₂O/mL/kg).
4. Chronic hypercapnic respiratory failure defined as $\text{PaCO}_2 > 60$ mmHg in the outpatient setting.
5. Home mechanical ventilation (non-invasive ventilation or via tracheotomy), not CPAP.
6. Actual body weight exceeding 1kg per centimeter of height.
7. More than 48 hours have passed since meeting inclusion criteria.
8. Severe hypoxemia with $\text{PaO}_2/\text{FiO}_2 < 80$ mmHg for > 6 hours at time of screening.
9. Severe hypercapnic respiratory failure with $\text{pH} < 7.15$ and $\text{PaCO}_2 > 60$ mmHg for > 6 hours at time of screening.
10. Expected mechanical ventilation duration < 48 hours at time of screening.
11. Confirmed diffuse alveolar hemorrhage from vasculitis.
12. Contraindications to limited anticoagulation (ex. active GI bleeding, bleeding diathesis).
13. Pregnancy—due to unknown effects of PaCO_2 changes on placental blood flow.
14. Respiratory failure known or suspected to be caused by COVID-19.

Eligible non-randomized patients will be identified and reasons for non-enrolment classified as:

1. Lack of consent from patient or substitute decision maker (specifying reason);
2. Refusal from attending physician (specifying reason);
3. Enrolment in a confounding RCT;
4. Research coordinator or device not available.

To better characterize the generalisability of our randomized population, baseline, demographic, and outcome data will be recorded on all eligible non-randomized patients.

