8.1.1 Stabilization and ECMO Initiation

If not already done, patients will be deeply sedated to a Sedation Assessment Scale (SAS) = 1 and then be paralyzed with a neuromuscular blocking agent (NMBA). Baseline usual care standard ventilation will then be set as follows:

- Mode: Volume Assist-Control
- FiO₂ 1.0;
- PEEP 10-15 cm H₂O or higher as needed to maintain SpO₂>92%;
- V_T = 6 ml/kg PBW and adjusted to maintain P_{PLAT} ≤ 30 cm H₂O
- Inspiratory to expiratory (I:E) ratio 1:1 to 1:3, avoiding auto-PEEP
- Respiratory rate set to match previous minute ventilation to maximum of 35 bpm and targeting a pH above 7.15

These initial adjustments may occur over a period of a few minutes to a couple of hours, depending upon the baseline V_T and the ability of the patient to tolerate sudden changes. In keeping with routine clinical practices, an arterial blood gas should be drawn within 1 hour of transitioning onto the study protocol to assess both oxygenation and ventilation.

As soon as the patient is stable on these standard settings, the clinical team will measure the patient's respiratory elastance using the following equation:

$$Elastance = \frac{Driving\ Pressure}{\frac{Tidal\ Volume}{PBW}} = \frac{P_{plat} - PEEP\ total}{\frac{VT}{PBW}}$$

If the patient's static driving pressure is 15 cmH₂O or lower, then re-assess patient within a 12-hour timeline for ECMO initiation whilst keeping the patient deeply sedated and paralyzed. If patient's static ΔP is 16 cmH₂O or higher, then proceed with cannulation and connection to the VV-ECMO circuit using sterile technique and monitoring according to usual practice (e.g. ultrasound-guided puncture, radiography, trans-esophageal echocardiography (TEE), or

fluoroscopic cannula positioning). We recommend use of the study-supplied dual-lumen bicaval Crescent cannula connected to the Nautilus oxygenator, but the clinical team may choose any VV-ECMO configuration that facilitates 3-5 L/min blood flow.

VV-ECMO will then be initiated with pump speed set to deliver blood flow of 3-5 L/min and sweep gas flow of 1 L/min of 100% oxygen.

The mechanical ventilator will then be adjusted as follows:

- Mode: Pressure Control
- FiO₂ 0.5
- Set Driving Pressure to 10
- PEEP 10-15 cm H₂O
- Inspiratory time 0.7-1 second
- Respiratory rate 10

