8.2 Control Group: Conventional Lung-Protective Ventilation (LPV)

Patients randomized to the control group will be treated with the same explicit standard ventilation protocol that we used to good effect in several recent multi-centre trials in ARDS. The overall goals for this strategy are to minimize volutrauma and atelectrauma to the extent possible with standard of care ventilation.

Volume Assist Control will be the default mode and will be set to achieve lower tidal volumes (6ml/kg PBW) and plateau pressures ($P_{PLAT} \leq 30$ cm H₂O). Other modes may also be used at the discretion of the attending physician. The same limits to P_{PLAT} and V_T apply regardless of ventilator mode. Only when the patient is being ventilated with Pressure Support of 10 cm H₂O support or less and with PEEP ≤ 8 cm H₂O and FiO₂ ≤ 0.4 will these thresholds (P_{PLAT} and V_T) no longer apply. We recommend that PEEP and FiO₂ be adjusted according to oxygenation targets using the higher PEEP-FiO₂ table, allowing for use of lower PEEP if clinically indicated. If the plateau pressure target is exceeded, V_T will be reduced as needed to a minimum of 4 ml/kg PBW, and/or PEEP reduced and FiO₂ increased as necessary to achieve $P_{PLAT} \leq 30$ cm H₂O while providing adequate oxygenation.

If a patient's state worsens and meets entry criteria from the EOLIA trial (persistence of either $\text{PaO}_2/\text{FiO}_2 < 80$ or $\text{pH} < 7.15$ and $\text{PaCO}_2 > 60$) they can receive VV-ECMO (a secondary outcome) at the discretion of the attending physician.

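### In the first 48 hours on ECMO, the experimental-arm deviation limits do not test the settings that define the treatment, so the adherence criterion can be met without separation between arms

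*Protocol*

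**What the plan says.** After ECMO starts, Protocol section 8.1.1 moves the experimental arm to pressure control with the instruction "Set Driving Pressure to 10", PEEP 10-15 and a rate of 10. Section 8.1.2 keeps these settings, with paralysis, for at least 48 hours. Once patients breathe spontaneously, and up to day 7, section 8.1.2 targets a dynamic transpulmonary driving pressure of at most 23 and a VT of at most 8 ml/kg.

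Control ventilation in section 8.2 "will be set to achieve lower tidal volumes (6ml/kg PBW"), with a plateau of at most 30.

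Section 10.7 ("Evaluate number of protocol deviations and their causes") counts VT above 8 or plateau above 30 in either arm, and a dynamic value above 23 in the experimental arm only. A deviation must hold over two consecutive data points and at least 48 hours. Section 10.13 item 1 calls adherence adequate if more than 80% of patients have under 10% of monitored values as major deviations. It does not split this by arm.

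The synopsis and section 4.2 name measured driving pressure in the ECMO group as an adherence focus. Section 10.6 keeps only "delivered tidal volumes in both groups and estimated" dynamic driving pressure, and section 10.7 sets no limit on the measured value.

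**The concern.** An adherence measure for a ventilation trial should fail when the assigned ventilation is not delivered. In the paralysed phase, two of the three experimental-arm limits are the control limits, and the third is more than twice the set driving pressure. A patient on ECMO but ventilated as a control can stay inside all three.

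The stakes are practical. Section 4.2 makes the roll-over of pilot patients into the definitive trial depend on feasibility, and adherence is one of the three criteria in section 10.13. Section 3.2 attributes an earlier null trial of CO2 removal to modest reductions in ventilation intensity. The present criterion could be declared adequate while that problem recurs.

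**Working it through.** **Inputs.** Entry elastance of at least 2.5 (section 5.3.2 excludes "normalized elastance < 2.5"). Cannulation proceeds at a static driving pressure of 16 or more (8.1.1). Settings come from 8.1.1 and 8.2, limits from 10.7, the pass mark from 10.13 and N = 72 from 10.1.

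**Formulas.** Driving pressure = plateau − PEEP = elastance × VT per kg (8.1.1). Dynamic value = (peak − PEEP) − 0.67 × occlusion pressure change (8.1.2). Under paralysis the effort term is zero.

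**The protocol's own figures.**
- Elastance: 15/6 = 2.5, which reproduces.
- Precision at 80% adherence, N = 72: 1.96 × √(0.8 × 0.2/72) = 9.2 points, consistent with the 10 points in section 10.1.

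**What the assigned setting delivers.** Driving pressure 10 gives VT 10/2.5 = 4.0 ml/kg, or 10/3.0 = 3.3 ml/kg.

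**A paralysed ECMO-arm patient kept at 6 ml/kg, PEEP 10.**

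| Elastance | Driving pressure | Plateau | Room below 23 for resistive pressure |
|---|---|---|---|
| 2.67 | 16 | 26 | 7 |
| 3.0 | 18 | 28 | 5 |
| 3.33 | 20 | 30 | 3 |

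No limit is crossed if resistive pressure stays within the last column.

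**Worked example.** VT 6, plateau 28, PEEP 11: driving pressure 28 − 11 = 17 and elastance 17/6 = 2.83. With peak 34 the dynamic value is 34 − 11 = 23, which is not above 23. Deviations: zero. Section 5.3.2 also excludes a dynamic value of 20 or less. If either value alone excludes, the same readings at screening need a peak above 11 + 20 = 31, so peaks above 31 and up to 34 both enter and pass.

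**Highest driving pressure that passes at elastance 2.5.**
- VT limit: 8 × 2.5 = 20.
- Plateau limit: 30 − 10 = 20 at PEEP 10; 30 − 15 = 15 at PEEP 15.
- Dynamic limit: 23 less any resistive pressure.
- Lowest of these: about 20 at PEEP 10 (with resistive pressure up to 3) and 15 at PEEP 15, against a setting of 10.

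**Pooled pass mark.** 0.8 × 72 = 57.6, so 58 patients must be adherent. Assuming 36 per arm and all controls adherent, 58 − 36 = 22 are needed in the experimental arm: 22/36 = 61%.

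**Persistence.** Data are daily (section 6.2), so 48 hours yields about two or three readings. The low-intensity phase may itself last only 48 hours, so a departure would have to fill that whole phase to count.

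**Per-arm precision.** 1.96 × √(0.8 × 0.2/36) = 13.1 points.

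**The case against.** The limits are not arbitrary. VT 8 and dynamic 23 are this arm's own targets in section 8.1.2 once patients breathe spontaneously, so section 10.7 follows the protocol for that phase. This stands, and it confines the point to the paralysed phase.

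Separation is partly covered elsewhere. Section 10.3 will describe delivered VT in both groups and the reduction in driving pressure. Sections 8.4 and 10.13 item 2 count premature ECMO stopping against a 10% limit. Both stand, but section 10.3 has no threshold, and the crossover rule does not catch a patient who stays on ECMO with conventional settings, nor does it name one never cannulated.

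A reader might infer that every conventionally ventilated patient would count as adherent. The documents do not support that. They give no resistive pressure. Over an assumed 0-7 cm H2O, a driving pressure of 16 always passes, 18 passes up to 5, and 20 only up to 3.

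A reader might also infer that a set driving pressure of 22 passes because it is below 23. At PEEP 10-15 it takes airway pressure to 32-37. If plateau approximates that pressure, the limit of 30 is breached.

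The control limit of 8 against a setting of 6 might look like the same fault. It can be read as a tolerance band, and section 8.2 lifts its thresholds on low pressure support. It is not part of this point.

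**Conclusion.** The point holds for the phase of at least 48 hours after ECMO start. There the section 10.7 limits do not test the section 8.1.1 driving pressure and rate. A patient ventilated to the control protocol can score zero deviations, with driving pressure at 1.5 to 2 times the setting (15/10 at PEEP 15, 20/10 at PEEP 10). Pooling over arms, the 48-hour persistence rule and the loss of measured driving pressure from sections 10.6 and 10.7 each weaken the criterion further.

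It would go too far to say that the adherence outcome can never show delivery of the treatment, because its limits fit the later spontaneous-breathing phase.

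The conclusion assumes passive patients, resistive pressure within the room shown, 36 patients per arm for the 61% figure, and that the major deviations of section 10.13 are those listed in section 10.7; no other definition is given.

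Severity: should-fix. This is one of three feasibility criteria in a descriptive pilot, and the primary accrual outcome is unaffected.

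**What to change.** 1. In section 10.7, score experimental-arm readings in the first 48 hours after ECMO start against the protocol's own section 8.1.1 settings, with a tolerance set by the sponsor. For that window, replace the 48-hour persistence rule with one that daily readings can meet. With two or three readings, a single one is 50% or 33% of values, so state how the 10% rule applies there.
2. Restore measured driving pressure to sections 10.6 and 10.7.
3. Apply and report section 10.13 item 1 by arm, and state that major deviations are those of section 10.7.
4. Make section 10.3 specific: report the between-arm difference in delivered VT, driving pressure and rate over the first 48 hours, with 95% intervals, as a descriptive feasibility outcome.

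The sponsor must reconcile sections 5.3.2, 8.1.1, 8.1.2 and 10.7. No clinical threshold is proposed here.

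Cost: wording only, since section 6.2 already has the ventilator data recorded daily. The adherence figure may be less favourable, and precision widens from about ±9 points pooled to about ±13 per arm.

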To be effective ECCO₂R must use efficient devices *and* target patients who cannot be safely ventilated with usual standard-of-care ventilation. The recently published REST trial used a low-flow, low-efficiency ECCO₂R device in 412 unselected patients with moderate-severe hypoxemic respiratory failure.[22] There was no difference in mortality between groups, likely driven by fact that only modest reductions in intensity of ventilation were achieved. Tidal volume was only 2 mL/kg lower in the ECCO₂R, and moreover this reduced driving pressure by only 3 cm of H₂O. Recent work from our group shows reductions in driving pressure drive mortality benefit from tidal volume reduction,[23] and that driving pressure is reduced most by ECCO₂R in patients with low respiratory system compliance (high elastance)[24].

The uncritical adoption of ECCO₂R is premature and problematic. Wide dissemination of VV-ECMO outside the severe ARDS population tested in EOLIA at this time would represent premature adoption of a complex technology without rigorous evaluation of associated risks and benefits. A systematic review of ECCO₂R identified 14 studies (2 RCTs) including only 495 patients and concluded that there is a “paucity of high-quality data and significant variation in technology used among studies”.[25] Recent editorialists on the REST Trial also conclude that “Future studies that harness the potential benefits of ECCO₂R without increasing the risk of other complications are needed”.

In summary, ECCO₂R can facilitate ultra-low intensity ventilation while simultaneously avoiding harmful hypercapnia and acidosis. At the current time the safest and most feasible manner to deliver CO₂ removal is through higher-flow VV-ECMO. This approach, termed ‘ultra-protective’ ventilation, may indeed improve outcomes in patients with moderate-severe ARDS. We therefore propose the Ultra-Low Tidal Volume Mechanical Ventilation in ARDS Through ECMO (ULTIMATE) Trial.

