4.2 The ULTIMATE Pilot Study

Before embarking on a definitive multinational trial to address the questions listed above, the ULTIMATE Pilot Study has these 3 specific feasibility objectives:

1. To assess the feasibility of recruiting 72 ARDS patients across sites over a period of 1-year of active enrollment per site, as well as estimate the rate of patient recruitment and understand barriers to recruitment;
2. To assess adherence to our explicit mechanical ventilation protocols, with particular focus on delivered tidal volumes in both groups and measured ΔP and estimated ΔP_{L-dyn} in the ECMO group; and lastly,
3. To measure and understand the reasons for crossovers in each group.

Our exploratory objectives include monitoring safety issues, by recording serious adverse events in both groups as well as quantifying cytokine levels to further understand the inflammatory processes involved.

If feasibility is demonstrated and major protocol changes are not required, patients randomized into the ULTIMATE Pilot Study will be rolled over and form the vanguard phase of the definitive ULTIMATE RCT.

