6.2 Study Schema

Required Procedures	Pre-Ventilation (Baseline)	Daily*	Day 1	Day 3	Day 7	ICU Discharge	At 6 months post-randomization (Phone Visit)
Window	N/A	N/A	N/A	N/A	N/A	N/A	±14 days
Consent & Randomization ¹	X						
Demographics ²	X						
Medical History ³	X						
Vitals ⁴	X	X					
Hemodynamics ⁵	X	X					
Respiratory Data ⁶	X	X					
Hematology ⁷	X	X					
Biochemistry ⁸	X	X					

Arterial Blood Gases (ABG) ⁹	X	X					
Pregnancy Test (urine/serum)	X						
Optional: Blood Sample Collection ¹⁰	X			X	X	X	
For the Control Arm: Conventional Lung Protective Ventilation ¹¹ per section 7.2		X					
For the Experimental Arm: ECMO Intervention ¹² per section 7.1		X					
MV Readiness to Wean	X	X					
Spontaneous Breathing Trial ¹³		X					
Sweep Gas Off Trials (SGOTs) ¹⁴		X					
HrQOL, Modified Rankin Scale and Vital Status							X ¹⁵
Glasgow Coma Scale and Sofa Score	X	X					
Serious Adverse Events ¹⁶			X				
Concomitant Medications ¹⁷	X						

¹ Consent should be obtained prior to any study-specific baseline assessments and according to site institutional timelines. Randomization in the ULTIMATE domain will occur for consenting eligible patients once elastance has been estimated as high (≥ 2.5 cmH₂O/ml/kg PBW) per indicated eligibility criteria.

² Demographics include age, gender, height, and weight. Race and ethnicity will be reported only for patients who have consented to the collection of this data.

³ Hospital admission (date/time), ICU admission (date/time), APACHE IV, Charlson Comorbidity Index, COVID-19 infection status

⁴ Vitals include temperature, heart rate, respiratory rate, and blood pressure.

⁵ Hemodynamics include BP, PAPm, PCWP, SvO₂ and will reported in the database if collected.

⁶ Respiratory data include mode of ventilation, FiO₂, PEEP, PIP, RR, ventilation rate, tidal volume, plateau and driving pressure, oxygen saturation, and expiratory occlusion pressure (P_{occ}).

⁷ Hematology reporting on Hg, WBCs, and platelets. If not done daily per clinical standard-of-care procedures, sites are not required to have these tests done exclusively for research purposes, and this will not be considered a protocol deviation.

⁸ Biochemistry will include reporting the following values: INR, PTT, activated clotting time, Fibrinogen, Antithrombin III, D-Dimers, plasma-free hemoglobin, sodium, glucose, creatinine, albumin, bilirubin, potassium, bicarbonate, creatinine kinase,

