8.1.2 Maintenance and Weaning of Ultra-Protective Ventilation

Deep sedation, paralysis, and these low-intensity mechanical ventilation settings will be maintained for at least 48 hours after ECMO initiation. The clinical team will make adjustments to the VV-ECMO settings to maintain the same PaCO₂, pH and PaO₂ and SpO₂ targets as above. These adjustments to VV-ECMO sweep gas or blood flow will be dictated by ABG results drawn as clinically indicated.

On study day 3, patients will then enter the maintenance and weaning phase – neuromuscular blockade will be discontinued, and lighter sedation levels (SAS 2-3) will be targeted unless otherwise decided by the attending physician.

During the first 7 days after randomization and once neuromuscular blockade is stopped and patients are making spontaneous breathing efforts, we will use sweep gas flow (primary) and sedation (secondary) to modulate spontaneous efforts to maintain low intensity ventilation, targeting the estimated dynamic trans-pulmonary driving pressure (ΔP_{L-dyn}) and tidal volume.

Clinicians will measure patient respiratory effort by calculating ΔP_{occ} (which is always zero or negative):[26]

- Perform expiratory hold and record trough pressure with next effort (record as = PEEP if no efforts made)
- Calculate $\Delta P_{occ} = \text{trough pressure} - \text{PEEP}$
- Calculate $\Delta P_{L-dyn} = (\text{Peak airway pressure} - \text{PEEP}) - 0.67 \times \Delta P_{occ}$

To maintain $\Delta P_{L-dyn} \leq 23$ cm H₂O while maintaining a V_T of 8 ml/kg PBW or lower, the treating team will adjust in the following order: a) the mechanical ventilator, b) the sweep gas flow, and c) sedation levels. After day 7 driving pressure and V_T targets, as well as sweep gas settings will be determined by the attending physician.

We will wean ECMO prior to liberating from mechanical ventilation and provide explicit protocols for weaning ECMO (See Manual of Procedures). Briefly, patients will be assessed daily for ability to discontinue ECMO – all patients who are not paralyzed and are breathing spontaneously on sweep gas flow of 4 L/min or less, and who are receiving an FiO₂ of ≤ 0.6 on the mechanical ventilator with a PaO₂/FiO₂ > 150 will undergo a trial of sweep gas off on ECMO. ECMO will be discontinued if patients tolerate sweep gas off for at least 12 hours (i.e., no significant hypoxemia, respiratory acidosis, or work of breathing).

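### Section 10.7 has no limit for the driving pressure of 10 cm H2O mandated during the first 48 hours on ECMO, so if 10.13 counts the 10.7 limits, a patient left at 16 can score as adherent.

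*Protocol*

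**What the plan says.** - **Mandated setting.** Once VV-ECMO is running, section 8.1.1 moves the experimental patient to pressure control and instructs "Set Driving Pressure to 10", with PEEP 10 to 15. Section 8.1.2 adds, for the deeply sedated and paralysed patient, that "these low-intensity mechanical ventilation settings will be maintained for at least 48 hours after ECMO initiation".
- **Later phase.** When paralysis has stopped and the patient makes efforts, 8.1.2 aims for a dynamic transpulmonary driving pressure of at most 23 and V_T of at most 8 ml/kg. This runs to day 7, after which the attending physician sets the targets.
- **Objective.** The adherence objective in 4.2 is worded "with particular focus on delivered tidal volumes in both groups and measured" driving pressure as well as its dynamic estimate in the ECMO group; the synopsis agrees. Section 10.6 reads "with particular focus on delivered tidal volumes in both groups and estimated" dynamic pressure only.
- **Limits.** Section 10.7 ("Evaluate number of protocol deviations and their causes") gives both arms V_T above 8 ml/kg and plateau above 30. The experimental arm also has dynamic pressure above 23. A deviation must span two consecutive data points over at least 48 hours.
- **Pass mark.** Section 10.13 item 1 calls adherence adequate when over 80% of patients each have under 10% of their monitored values as major deviations.

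**The concern.** The limits of 8 and 23 are the targets of the later, spontaneously breathing phase. The plateau limit is shared with the control arm. The setting that defines the intervention in its first 48 hours therefore has no limit of its own, although the objective in 4.2 says that measured driving pressure is to be assessed.

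Section 3.2 explains why this matters. It attributes an earlier neutral trial of low-flow CO2 removal to the fact that "only modest reductions in intensity of ventilation were achieved", with driving pressure only 3 cm H2O lower. An adherence criterion for this pilot should be able to detect the same failure. As written, it can be satisfied by a patient whose driving pressure has not fallen at all in the mandated window. Feasibility in this pilot is one of the conditions for carrying its patients into the definitive trial (4.2).

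**Working it through.** **The plan's own figure.** Section 10.1 says 72 patients give an adherence rate of 80% within about 10 points. The 95% half-width is 1.96 × √(0.8 × 0.2 / 72) = 9.2 points, so this figure is sound. The question is what is being counted.

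**Inputs.** Cannulation at a static driving pressure of 16 or more on V_T 6 ml/kg; set driving pressure 10; PEEP 10 to 15 (all 8.1.1). Limits: V_T 8, plateau 30, dynamic pressure 23 (10.7).

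**Formulas for a paralysed patient on pressure control.**
- Normalised elastance at the threshold = 16 / 6 = 2.67.
- V_T = driving pressure / elastance.
- Plateau = PEEP + driving pressure.
- Dynamic pressure = (peak − PEEP) − 0.67 × occlusion pressure. With no effort the last term is 0 (8.1.2), so it equals the driving pressure.

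**At the mandated 10:** V_T = 10 / 2.67 = 3.75 ml/kg. The limit of 8 is 8 / 3.75 = 2.1 times that.

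**At 16, no fall:** V_T = 6.0 and dynamic pressure = 16, both inside their limits. Elastances of 2.5, 3.0 and 3.5 give V_T 6.4, 5.3 and 4.6, so V_T does not bind there either. Only plateau can bind:

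| PEEP | Plateau at 16 | Limits broken at 16 | Largest whole driving pressure inside all limits (V_T) |
|---|---|---|---|
| 10 | 26 | 0 of 3 | 20 (7.5) |
| 11 | 27 | 0 of 3 | 19 (7.1) |
| 12 | 28 | 0 of 3 | 18 (6.75) |
| 13 | 29 | 0 of 3 | 17 (6.4) |
| 14 | 30 | 0 of 3 | 16 (6.0) |
| 15 | 31 | 1 of 3 | 15 (5.6) |

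The intended fall is 16 − 10 = 6 cm H2O. The fall needed to stay inside the limits is 0 at PEEP 10 to 14 and 1 at PEEP 15.

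**What a 48-hour limit could change.** More than 80% of 72 means 58 adherent (80.6%); 57 (79.2%) fails, so 15 non-adherent patients reverse the result. The protocol gives no rate of patients left at 16, so a range is needed. If 0, 5 or 10 patients are non-adherent for other reasons, it takes 15, 10 or 5 of the 36 experimental patients (42%, 28%, 14%) left at 16. At PEEP 10 to 14 the present limits count none of them.

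**Dilution.** These counts require the 48-hour limit to be decisive for the patient. Assume three monitored values per day plus two driving-pressure values. Over D days the two bad values make up 2 / (3D + 2): 2/20 = 10.0% at D = 6 and 2/23 = 8.7% at D = 7. From day 7 they fall under the 10% allowance, so a limit added without a patient-level rule would not change the score of a patient monitored that long.

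**The case against.** **Limits may be looser than targets.** The control arm aims for 6 ml/kg but is flagged only above 8, so 10.7 may be meant to catch gross departures. That is fair as a principle. But 8 / 6 = 1.33, whereas the experimental limits tolerate 20 / 10 = 2 times the mandated driving pressure at PEEP 10 and 1.5 times at PEEP 15. The variable named in 4.2 has no limit in this phase, only an indirect cap.

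**10.13 does not say that 10.7 defines a major deviation.** This stands. A counting rule could sit in an analysis plan or the Manual of Procedures. But 10.7 is the only list in the protocol, and a plan written from 10.6 and 10.7 would inherit the gap.

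**Poor separation would be seen.** Section 10.3 assesses tidal volume and the reduction in driving pressure, and rollover under 4.2 also requires that no major protocol changes are needed. Both points stand. A reader might infer that adherence alone would carry the pilot forward; the protocol does not say so. What is missing is a pass mark for the mandated setting.

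**ECMO status.** A reader might also infer that stopping ECMO escapes scrutiny because it has no ventilation limit. It does not: the second item of 10.7 classifies crossovers, 8.4 makes premature stops deviations, and 10.13 item 2 judges them against a 10% mark. Footnote 12 of the schema mainly tells sites to continue ECMO after a failed sweep-off trial, and section 8.1.2 ends study-mandated ECMO procedures after 14 days. No change is needed there.

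**Conclusion.** The point holds for driving pressure in the first 48 hours on ECMO. Section 4.2 and the synopsis include measured driving pressure in the adherence objective, 10.6 leaves it out, and 10.7 has no limit matching the mandated setting. A paralysed patient at 16 breaks no limit at PEEP 10 to 14 and one at PEEP 15.

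The arithmetic assumes no effort, no auto-PEEP, and plateau equal to PEEP plus set pressure. The step to the feasibility mark assumes that 10.13 item 1 counts the 10.7 limits. The numbers that would reverse the mark (5 to 15 of 36) also need a patient-level rule and are a range, not a forecast. It would be tempting to say that the pilot will pass despite weak separation; nothing in the protocol says how many patients would remain off target, so that cannot be claimed.

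This should be corrected, but it does not endanger the pilot's data.

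**What to change.** 1. **Section 10.6:** restore measured driving pressure in the ECMO group, as in 4.2.
2. **Section 10.7:** add an experimental-arm limit for the first 48 hours after ECMO initiation: plateau minus PEEP above a prespecified value near 10 on both daily recordings. A value of 12 is one possibility, for the sponsor to set. It is the highest whole number that requires a fall of more than 3 from 16 (16 − 12 = 4; 13 would require only 3), and it corresponds to V_T 12 / 2.67 = 4.5 ml/kg.
3. **Section 10.13 item 1:** count a patient who breaks this limit as non-adherent, or report the limit as its own proportion with its own mark, so that later values do not dilute it. State there that the 10.7 limits are the major deviations.

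**Cost.** These are wording changes in three sections. The study schema already collects "ventilation rate, tidal volume, plateau and driving pressure, oxygen saturation" daily, so no patients, procedures or measurements are added. The adherence mark becomes harder to meet. If the limit is reported separately in the 36 experimental patients, its precision is lower: 1.96 × √(0.16 / 36) = 13.1 points at 80%, against 9.2 in all 72.
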